3.2 Project contents

The study is designed as a prospective, multi-centre, post-market, real-world observational registry study. Continuous enrollment is to be conducted for all subjects treated with Minos™ Abdominal Aortic Stent-Graft and Delivery System who meet the inclusion criteria and who voluntarily consent to participate in the study. An enrollment duration period of 24 months is expected for this project and initially, 200 subjects (170 in China and at least 30 in Europe) are to be enrolled. Patient follow up – including CT imaging - will be undertaken in accordance with the usual standard of care at participating sites, and is expected to occur at 30 days, 6 months, 12 months and 2-5 years post-procedure.

1. Primary endpoint

- Technical success rate at 12 months

2. Secondary endpoints

- Incidence of major adverse events at 30 days
- Immediate technical success rate
- Incidence of successful aneurysm treatment at 2-5 years
- All-cause mortality up to 5 years post-procedure
- Aortic aneurysm related mortality up to 5 years post-procedure
- Secondary intervention rates up to 5 years post-procedure
- Aneurysm diameter and variation in aneurysm diameter from 30 days to 5 years post-procedure
- Incidence of type I, III endoleaks from 30 days to 5 years post-procedure
- The incidence rate of stent migration, fracture, stenosis, occlusion and distortion from 30 days to 5 years post-procedure

3. Other endpoints: technical success rate of Hercules balloon and incidence of balloon rupture, where applicable.

In this study, immediate technical success rate, technical success rate at 12 months, secondary intervention rate, aneurysm diameter and variation in aneurysm diameter, and the incidence of type I and III endoleaks are used as efficacy indicators of the Minos™ Abdominal Aortic Stent-Graft and Delivery System. The incidence of 30-day major adverse events, all-cause mortality, aneurysm related mortality, stent migration, stent fracture, stenosis, occlusion and distortion are used as safety indicators of the Minos™ Abdominal Aortic Stent-Graft and Delivery System.

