7.1.5 Primary endpoint

Successful aneurysm treatment: on the basis of technical success and during the follow-up period, the absence of aneurysm rupture, continuous type I and III endoleaks after operation, aneurysm enlargement (aneurysm diameter increased by more than 5mm), secondary intervention due to endoleak, stent occlusion or migration, including open surgery and endovascular surgery. Expected secondary interventions will not be included in the analysis.

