Endoleak: recorded after surgery according to imaging appearances. Adjuvant therapy such as balloon dilatation due to intraoperative endoleak shall not be included in the analysis. Type I endoleaks are leaks at the proximal or distal attachment sites. Type II endoleaks are caused by retrograde flow through collateral vessels into the aneurysm sac. Type III endoleaks are holes, defects, or separations in the stent-graft material. Type IV endoleaks represent porous graft walls. Endoleaks observed in the same subject at different follow-up timepoints without and which have not been treated shall be calculated once.

Stent migration: movement of stent greater than 10 mm.

Stent fracture: fracture of the metal wire of the stent framework.

Stent stenosis and occlusion: stenosis of the internal diameter of the covered section of the stent is a narrowing of $\geq 50\%$ as seen on imaging; stent occlusion refers to 100% stenosis of stent detected on imaging.

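### Section 7.1.5 leaves *continuous* endoleak undefined and, on its natural reading, counts stent occlusion and migration as failures only when they led to a secondary intervention

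*Protocol*

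**What the plan says.** Sections 3.2 and the Protocol Summary name the primary endpoint "Technical success rate at 12 months". Under the primary endpoint heading, section 7.1.5 defines something with another name and no time point: "Successful aneurysm treatment: on the basis of technical success and during the follow-up period, the absence of aneurysm rupture". The list of absences continues with "continuous type I and III endoleaks after operation", aneurysm growth of more than 5 mm, and "secondary intervention due to endoleak, stent occlusion or migration, including open surgery and endovascular surgery". It closes with "Expected secondary interventions will not be included in the analysis". Neither *continuous* nor *expected* is explained anywhere in the protocol.

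Section 7.1.6 defines the same findings for the secondary endpoints without any condition on persistence or treatment:

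- "Endoleak: recorded after surgery according to imaging appearances"
- "Stent migration: movement of stent greater than 10 mm"
- "stent occlusion refers to 100% stenosis of stent detected on imaging"

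Successful aneurysm treatment at 2–5 years is also a secondary endpoint in section 3.2. Section 7.1.6 gives it no definition of its own, so the wording of 7.1.5 has to serve there as well.

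**The concern.** Two device findings may fail to register as failures in the headline rate.

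The first is a type I or III endoleak that cannot yet be shown to be continuous. Scheduled imaging is at 30 days, 6 months and 12 months. A leak first seen at 12 months has no later scan by that time point. Under note 4 to the flow chart in section 7.2, CT may be omitted or replaced by ultrasound where that is local practice, so whether persistence can be shown depends on how a site images.

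The second is an occluded stent or a migration above 10 mm that nobody treats. If these count only through a secondary intervention, the outcome turns on the site's decision to intervene. Section 7.1.3 promises blinded reading of the follow-up images to limit bias, but for these two components the blinded read would not decide the outcome.

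At stake is what the success rate means. Two sites with the same imaging results could report different rates because they re-treat or scan differently. The same subject could also be a success in the main table and an occlusion or migration in a secondary table at the same visit.

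**Working it through.** **Step 1: apply the two sections to the same subject.** Each row assumes no rupture, no enlargement above 5 mm and no other event.

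| Finding by the 12-month visit | Section 7.1.5 | Section 7.1.6 |
|---|---|---|
| Type I/III leak on an earlier scan, still present at 12 months | Failure on any reading | Endoleak |
| Type I/III leak that led to a secondary intervention | Failure, unless the intervention is classed as expected | Endoleak; secondary intervention |
| Type I/III leak first seen at 12 months, not treated | Open; not a failure if *continuous* needs more than one scan | Endoleak |
| Occlusion or migration >10 mm that led to a secondary intervention | Failure, unless classed as expected | Occlusion or migration; secondary intervention |
| Occlusion or migration >10 mm, not treated | Success on the natural reading | Occlusion or migration |

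The third and fifth rows are the problem. In the fifth, the closing words of the phrase (open and endovascular surgery) describe the intervention, so endoleak, occlusion and migration are its causes. Treating occlusion and migration as separate items in the list of absences is grammatically possible but less natural.

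**Step 2: compare with the rest of the protocol.** Immediate technical success in section 7.1.6 requires the absence of occlusion at the procedure, whether or not anyone acts on it. Section 13.1 lists type I/III endoleak, stent migration and limb occlusion among device-related adverse events, again without a treatment condition. The treatment condition is therefore peculiar to 7.1.5.

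**Step 3: size.** The documents give no rate for either group, so the effect can only be shown over an assumed range.

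Inputs: N = 200 (section 8.3, which gives no statistical inputs from which to reproduce it); exact binomial 95% intervals (section 8.2); an illustrative starting rate of 89%, borrowed from the earlier study in section 4. That figure reproduces: 121/136 = 88.97%, exact 95% interval 82.5% to 93.7%. Its definition of clinical success is not shown, so it serves only as a starting value.

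Starting count: 0.89 × 200 = 178. If a net share r of all subjects moves from success to failure, k = 200r and the rate becomes (178 − k)/200.

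| Assumed r | k | Success rate | Exact 95% interval |
|---|---|---|---|
| 0 | 0 | 89.0% | 83.8–93.0% |
| 1% | 2 | 88.0% | 82.7–92.2% |
| 2% | 4 | 87.0% | 81.5–91.3% |
| 3% | 6 | 86.0% | 80.5–90.5% |
| 5% | 10 | 84.0% | 78.2–88.8% |

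The chance that at least one of 200 subjects is affected is 1 − (1 − r)^200. At r = 1% this is 1 − 0.99^200 = 87%; at r = 2% it is 98%. If such cases occur at even these low rates, the scoring question will very probably arise.

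**The case against.** Several stronger readings are tempting, and the documents do not support them.

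- A reader might infer that an endoleak counts only if it is continuous. It does not: the same sentence also fails a subject for an intervention due to endoleak, for enlargement and for rupture.
- A reader might infer that a leak first seen at 12 months is definitely scored as success. The text leaves this open. *Continuous* after the operation could instead separate a postoperative leak from an intraoperative one dealt with by ballooning, which section 7.1.6 leaves out of the analysis. Nor must a re-intervention prompted by that scan fall too late: the visit window is ±60 days and 7.1.5 sets no 12-month cut-off.
- A reader might infer that failures are concealed. They are not: type I/III endoleak, migration and occlusion are separate secondary endpoints from 30 days to 5 years.
- A loss of several percentage points might be claimed. Any such figure rests on assumed rates and on no overlap with other failure criteria.

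It is also fair to say that an intervention-driven composite is a legitimate choice, that section 8.3 describes a study without a formal hypothesis test, and that no performance goal exists for a shift to cross. A SAP could define *continuous*.

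All of this limits the severity. It does not remove the point. A SAP could not make an untreated occlusion a failure without departing from the natural meaning of 7.1.5, and reporting the events elsewhere does not change what the headline rate measures. If the sponsor intended the other parsing, the sentence still needs rewriting, because two analysts could score one subject differently.

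**Conclusion.** The point holds in a limited form. Section 7.1.5 does not settle how a type I or III endoleak first seen at 12 months is scored, and on the ordinary reading it is not a failure. On the natural reading, an untreated occlusion or migration above 10 mm is a success. The rate therefore depends partly on site scanning and re-treatment practice, and the bias is likely to be upward.

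Its size is unknown. Each 1% of 200 subjects affected, with no other failure criterion met, is 1 percentage point; the illustrated 1% to 5% is an assumption. The conclusion on occlusion and migration rests on how the list is parsed. The link to 12 months rests on the definition's place under the primary endpoint heading, since the definition itself names no time point.

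This should be corrected before the 12-month analysis. It does not undermine the registry, which is descriptive and reports the same events separately.

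**What to change.** In section 7.1.5:

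1. State that a type I or III endoleak present on the scan at the assessed time point (12 months; likewise each of years 2–5), or one that led to a secondary intervention, is a failure. This replaces *continuous*. An untreated leak seen earlier but gone by the assessed scan would then not be a failure at that time point, so the sponsor should confirm that this is intended.
2. State that imaging-detected stent occlusion and migration above 10 mm, as defined in 7.1.6, are failures whether or not treated. If the sponsor keeps the intervention-driven composite as the main definition, report this imaging-based version alongside it.
3. Keep secondary intervention as a separate criterion, and say which interventions are *expected*.
4. Reconcile the endpoint's name and time point between sections 3.2 and 7.1.5.

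Do not add a last-available-scan rule here. It would bring a missing-data rule into the endpoint definition; subjects without a scan belong under section 8.5.

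The cost is modest. The imaging findings are already collected for the secondary endpoints, and no patient's management changes. The reported success rate may be slightly lower. Because the wording concerns an endpoint, the after-the-fact notice for non-substantive changes (sections 12.1 and 14) would not cover it; an amendment with written ethics approval is needed (section 12.2). Screening was expected from October 2021, so the amendment should record that the change was made without reference to accumulated success rates.

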Pre-clinical testing was completed prior to CE marking and approval for use in the EU and a domestic pre-clinical investigation of the device in human patients was conducted following successful preclinical trials and testing. A total of 137 patients were enrolled, with an average age of 69.5 years. The 12-month clinical success rate was 89% (121 / 136), the rate of 30-day major adverse events was 1.5% (2/136), the 12-month all-cause

mortality was 7.4% (10 / 136), the aneurysm related mortality was 0.7% (1/136), and the safety and effectiveness have been verified. Therefore, the Minos™ Abdominal Aortic Stent-Graft and Delivery System has been authorized with the Registration Certificate for Medical Device of the People's Republic of China in March 2019, Certificate No.: GXZZ 20193130182. And was CE-Marked in September 2019, Certificate No.: M.2019.106.12584. On this basis, this post-market registry has been commenced to observe the medium and long-term clinical outcomes of Minos™ Abdominal Aortic Stent-Graft and Delivery System in the treatment of AAA in a real-world patient population.

References

- [1] 中华医学会外科学分会血管外科学组腹主动脉瘤诊断与治疗指南. 中国实用外科杂志, 2008, 28(11): 916-917.
- [2] YII M K. Epidemiology of abdominal aortic aneurysm in an Asian population. ANZ J Surg, 2003, 73(6): 393-395
- [4] Lederle F A , Freischlag JA , Kyriakides T C , et al. Long-term comparison of endovascular and open repair of abdominal aortic aneurysm. N Engl J Med, 2012, 367 (21): 1988-1997.
- [6] Barbanti M, Binder RK et al. Impact of low-profile sheaths on vascular complications during transfemoral transcatheter aortic valve replacement. EuroIntervention. 2013 Dec; 9(8):929-35.

5、 Product features, structural composition, working principle, mechanism of action and scope of study

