7.1.6 Secondary endpoints

30-day major adverse events: events that meet one of the following criteria during the study:

- All-cause mortality: death of any cause occurring within 30 days of procedure.
- Intestinal ischemia: lack of sufficient blood flow in the intestine, requiring intensive drug treatment or surgical/intravascular intervention treatment.
- Myocardial infarction: the increase of one or more cardiac biomarkers (especially troponin) with evidence of myocardial ischemia: ECG changes suggesting new ischemia, or imaging evidence.
- Paraplegia: severe paralysis of lower limbs.
- Kidney failure: GFR < 15ml/min, requiring permanent dialysis, renal transplantation, or death due to renal insufficiency.
- Respiratory failure: pneumonia or respiratory failure requiring ventilator support for more than 24 hours after surgery.
- Stroke: symptoms lasting 24 hours due to cerebrovascular diseases such as hemorrhage, embolism or thrombosis.
- Blood loss > 1000 ml: estimated intra-procedural blood loss > 1000 ml.

Immediate technical success: successful introduction and withdrawal of stent graft and delivery system, with accurate positioning of stent graft, normal stent shape, no distortion, bending, stenosis and occlusion, and no accidental coverage of internal iliac artery or visceral artery.

All-cause mortality: death from any cause.

Aneurysm related death: death caused by rupture of abdominal aortic aneurysm or any operation to treat abdominal aortic aneurysm. All deaths shall be judged by the Clinical Events Committee (CEC) to determine the relevance of aneurysm, instruments or surgery.

Secondary intervention: including open and intracavitary intervention. Open surgery: Open surgery performed at any time to address a failure of endovascular treatment due to failure of stent implantation or placement, complications or other clinical conditions, or after the initial success of endovascular treatment. Secondary endovascular intervention: any intravascular surgical intervention performed to resolve complications such as endoleak, aneurysm expansion, stent occlusion, stent migration and stent defect after the implantation of Minos™ system.

Change in aneurysm diameter: including “enlargement”, which refers to an increase of aneurysm diameter greater than 5mm; “reduction”, which refers to a reduction of aneurysm diameter greater than 5mm; and “stable”, which refers to a change in aneurysm diameter less than or equal to 5mm.

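### The success definition in 7.1.5 omits death and exempts undefined 'expected' reinterventions, so some patients with a bad outcome of the repair can be scored as treatment successes

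*Protocol*

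**What the plan says.** Section 7.1.5, headed as the primary endpoint, defines successful aneurysm treatment as "on the basis of technical success and during the follow-up period, the absence of aneurysm rupture, continuous type I and III endoleaks after operation", no enlargement of more than 5 mm, and no "secondary intervention due to endoleak, stent occlusion or migration, including open surgery and endovascular surgery". It closes with the exemption "Expected secondary interventions will not be included in the analysis". No other section defines *expected* for this purpose.

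Section 7.1.6 supplies the related definitions:

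- Immediate technical success is purely procedural (delivery, position, shape and patency of the graft, no unintended coverage of branch arteries). Survival is not required.
- "Aneurysm related death: death caused by rupture of abdominal aortic aneurysm or any operation to treat abdominal aortic aneurysm". The Clinical Events Committee (CEC) judges every death.
- Secondary endovascular intervention covers procedures "performed to resolve complications such as endoleak, aneurysm expansion, stent occlusion, stent migration and stent defect". Open surgery is defined more broadly still. Neither part separates expected from unexpected interventions.

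The Protocol Summary and section 3.2 give the primary endpoint a different name, "Technical success rate at 12 months", and list successful aneurysm treatment at 2 to 5 years as a secondary endpoint. Section 3.2 places both mortality endpoints among the safety indicators.

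**The concern.** A composite called successful treatment should not be satisfied by a patient killed by the treatment. Under 7.1.5 it can be. If the graft is placed correctly and the patient then dies of the operation without rupture, persistent leak, growth or a listed reintervention, no failure criterion is met.

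The exemption has a similar effect. It does not require the intervention to have been planned beforehand, so the label can be given once the outcome is known. Section 20.1 uses *expected* for adverse events that are anticipated with the device, and section 13.1 lists type I/III endoleak, migration and limb occlusion as device-related complications. On that usage, the reinterventions that 7.1.5 counts as failures could be called expected.

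Both features push the rate in the favourable direction. The same definition serves the 2 to 5 year endpoint, so the problem carries forward.

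**Working it through.** **Which patients are affected**

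- *Death after the index repair, technically successful, no listed event:* meets no failure criterion in 7.1.5. This is the main gap.
- *Death from rupture:* already a failure, through rupture.
- *Death after reintervention for endoleak, occlusion or migration:* already a failure through the reintervention, unless that is called expected.
- *Reintervention for expansion:* already a failure if growth exceeds 5 mm.
- *Reintervention for a graft defect with a leak:* already a failure, because 7.1.6 classes leaks through defects in the graft material as type III.
- *Reintervention for stenosis short of occlusion* (7.1.6 sets stenosis at 50% narrowing or more and occlusion at 100%), *or for a stent defect without a type I/III leak:* within 7.1.6, but not a failure in 7.1.5.

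**Inputs**

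Section 4 gives 12-month results of the earlier study in 136 patients, and section 8.3 gives N = 200. The stated rates reproduce (exact 95% intervals):

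- Clinical success: 121/136 = 89.0% (82.5 to 93.7)
- All-cause death: 10/136 = 7.4% (3.6 to 13.1)
- Aneurysm-related death: 1/136 = 0.7% (0.02 to 4.0)

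**Expected deaths by 12 months among 200**

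- All causes: 200 × 10/136 = 14.7, about 15 (7 to 26 over the interval)
- Aneurysm related: 200 × 1/136 = 1.5, so 1 to 2 (0 to 8 over the interval)

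**Aneurysm-related death counted as failure**

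One or two patients move: 1/200 = 0.5 point, 2/200 = 1.0 point. This is a maximum at the earlier rate, because some of these deaths would follow rupture or a listed reintervention and already count. At the upper confidence limit, 8/200 = 4 points.

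**Handling of all deaths**

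Assume 15 non-fatal failures and 15 deaths without a listed event:

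- Deaths scored as success: (200 − 15)/200 = 92.5% (87.9 to 95.7)
- Deaths excluded: (200 − 15 − 15)/(200 − 15) = 170/185 = 91.9% (87.0 to 95.4)
- Deaths scored as failure: (200 − 15 − 15)/200 = 85.0% (79.3 to 89.7)

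The span between the extremes is 15/200 = 7.5 points, whatever the number of non-fatal failures. With 5 such failures it is 97.5% to 90.0%, and with 22 it is 89.0% to 81.5%.

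**Exempted reinterventions**

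Each one that was the patient's only failure event adds 1/200 = 0.5 point if the event is ignored. With 15 failures at the start (92.5%):

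- 2 exempted: 187/200 = 93.5%
- 5 exempted: 190/200 = 95.0%
- 10 exempted: 195/200 = 97.5%

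The numbers 2, 5 and 10 are assumptions. If the exemption instead removes the patient from the denominator, the results are 185/198 = 93.4%, 185/195 = 94.9% and 185/190 = 97.4%. The rate rises by nearly as much on either reading.

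**The case against.** Mortality is not hidden. All-cause and aneurysm-related death are named secondary endpoints, 30-day death is part of the major adverse event composite, the CEC judges every death, and section 8.2 plans Kaplan-Meier analyses. Keeping efficacy and safety apart is a legitimate choice in a descriptive registry without a hypothesis test. This stands, and it confines the defect to the success rate.

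A reader might infer that the protocol scores these deaths as successes. It does not say so. A patient with no 12-month assessment might be treated as missing or left out of the per-protocol set, which requires observable main indicators (8.1). Section 8.5 does not settle the matter, since it imputes only after premature withdrawal and refers back to a strategy that the protocol does not set out. What is supported is that such patients *can* be scored as successes.

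The gap against 7.1.6 is also narrower than a comparison of the two lists suggests, as the working shows. And *expected* may well have been meant as planned, but the text does not say that.

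An unseen statistical analysis plan might give scoring rules. The components and the exemption are fixed in the protocol, however, and a later document should not silently override them.

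**Conclusion.** The concern holds for the 7.1.5 success rate. The definition has no death component, and its exemption can be applied after the outcome is known. At the earlier study's rates, the omission of aneurysm-related death is worth at most about 0.5 to 1 point, and each exempted sole-failure reintervention 0.5 point. The unstated handling of all deaths is worth 7.5 points, on the assumption of 15 deaths without a listed event. Most of that span concerns deaths unrelated to the aneurysm, and whether these belong in the primary composite is debatable.

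Two stronger readings are not supported. A reader might infer that the result cannot be compared with the earlier 89%, or that leaving out deaths would have raised that figure to 131/136 = 96.3%. The protocol does not give the earlier definition of success or say how its 10 deaths were scored. A reader might also project aneurysm-related deaths to 5 years, but that would extrapolate one event and include rupture deaths that already count as failures.

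The conclusion applies to 7.1.5 as the operative definition. The different name in the Summary and section 3.2 must be reconciled with it.

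**What to change.** In section 7.1.5:

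1. Count CEC-adjudicated aneurysm-related death, as defined in 7.1.6, as failure.
2. Replace the reintervention list by any secondary intervention that meets the 7.1.6 definition.
3. Limit the exemption to staged procedures documented as planned before the index procedure ended, and state that the event, not the patient, is disregarded.
4. Report other deaths before 12 months as a separate category, with a sensitivity analysis that counts them as failures.
5. Use one name and one definition for the primary endpoint in the Summary, section 3.2 and section 7.1.5.

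The cost is revised wording, with the ethics committee approval that section 12.2 requires for protocol revisions, and one data field for planned staged procedures. Screening was expected from October 2021 (7.1.4), so for patients already treated that field has to be filled from source records. CEC review of deaths is already planned. The headline rate will be slightly less favourable.
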